"Efficacy of memantine compared with sodium valproate in the prophylactic treatment of migraine" Randomized controlled clinical trial.

NEUROLOGY DEPARTMENT

ID:74-19

NCT04698525

Study Protocol document date: February 15, 2019; Statistical Analysis Plan document date: January 15, 2020; Informed Consent Form document date: February 5, 2019.

HOSPITAL CENTRAL
“DR. IGNACIO
MORONES PRIETO”

SAN LUIS POTOSÍ AUTONOMOUS UNIVERSITY

MEDICAL SCHOOL

CENTRAL HOSPITAL "DR. IGNACIO MORONES PRIETO" CENTRAL HOSPITAL

Thesis to obtain the diploma in the specialty of Neurology.
"Efficacy of memantine compared with sodium valproate in the prophylactic treatment of migraine" Randomized controlled clinical trial.

[name]

ASSESOR
[name] [name]

CO - CONSULTANTS
[name] [name]
[name] [name].

San Luis Potosí January 15, 2020

SUMMARY

Objectives

To compare the efficacy of Memantine versus sodium Valproate as a prophylactic treatment of episodic migraine for three months. Evaluating efficacy (measured in reduction in the number of migraine attacks per month) and safety (measured in frequency and severity of adverse events), as well as response rate.

Subjects and methods

The prospective, randomized, double-blind, controlled clinical trial was conducted with patients who attended the outpatient clinic, either by referral or by the Emergency Department of the Neurology Service of the Central Hospital. Participants were randomized into two groups, the Memantine group received doses of 10 mg twice a day and the Sodium Valproate group received 500 mg twice a day, both groups for 3 months.

Results

A total of 33 patients were included in the study, 27 of them concluded the study; 14 in the Memantine group and 13 in the Sodium Valproate group. The Memantine group with mean number of migraine attacks per month prior to treatment of 5.31 ($SD \pm 1.54$) and after three months of treatment, mean number of migraine attacks per month 0.93 ($SD \pm 1.49$) with a decrease of 4.21 ($SD \pm 1.76$) migraine attacks $p <<0.001$. In the VPA group the mean number of migraine attacks before treatment was 5.35 ($SD \pm 1.11$) migraine attacks per month and after three months of treatment the mean number of migraine attacks per month was 0.77 ($SD \pm 1.16$), with a decrease of 4.5 ($SD \pm 1.39$) migraine attacks $p <<0.001$. All 27 patients had a good response rate. Adverse effects were infrequent in both groups and of minimal severity.

Conclusions

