- **Migraine disability:** defined numerically according to the MIDAS (Migraine Disability Assessment) survey, (where 0-5=no disability, 6-10 points mild disability, 11-20 points moderate disability, and >21=severe disability).

DEDICATION

BACKGROUND

Migraine is a primary headache, currently one of the three most disabling diseases worldwide.¹ It has an annual and lifetime prevalence of 18% and 33% in women, and 6 to 13% in men respectively, with a predominance in women (3:1).² The age of onset with the highest prevalence is 25 to 55 years.³

Migraine is described by the International Headache Society (IHS) as recurrent episodes of headache lasting from 4 to 72 hours, characterized by: unilateral localization, pulsating character, moderate or severe intensity, worsening with physical activity and association with nausea or photophobia and/or phonophobia. The IHS also classifies migraine according to the frequency of attacks: episodic migraine when the headache occurs less than 15 days a month, and chronic migraine, when the headache occurs 15 or more days a month for three months, and for at least 8 days a month with migraine headache characteristics.⁴

The subtypes of migraine with respect to its clinical presentation are: migraine with aura and without aura.⁴ Up to one third of migraine patients present with aura, with visual symptoms being the most frequent.⁵

Four phases have been identified during migraine: prodromal phase, aura, headache, and postdrome. The prodromal phase is characterized by premonitory symptoms hours before the headache, including difficulty concentrating, irritability, fatigue, repetitive yawning, neck stiffness and photophobia.⁶

Aura is characterized by recurrent episodes, lasting from 5 minutes to 60 minutes, with unilateral transient visual, sensory or other central nervous system symptoms, which develop progressively, usually preceding headache and migraine-associated symptoms.⁴ The genesis of aura is NMDA (N-methyl-D-aspartate) receptor activation and disseminated cortical depression. Disseminated cortical depression is an extreme depolarization of the cell membranes of glia and neurons that produces alteration of the ionic gradient, an increase in extracellular potassium concentrations, glutamate release, and a transient increase followed by a decrease in cerebral blood flow.⁶

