Sample size calculation

Normal distribution model: $x=Z(c/100)^2 r(100-r)$. $n=Nx/((N-1)E^2+x)$ $E=\text{Sqrt}[(N-n)x/n(N-1)]$. With a margin of error of 5%, a confidence level of 95%, with a prevalence of migraine in the general population of the State of San Luis Potosi of 271800 with a distribution response of 15%.¹⁹ The recommended sample size is 196 participants. Due to the fact that a pilot study will be conducted, 10% of the sample size will be taken to make it representative, a sample size of 20 participants for each group is decided.²⁰

Descriptive statistical analysis of the variables of interest will be performed. For continuous variables, analysis will be performed using the Student's t-test. The number of participants (n) and the final analysis was calculated using R (56). Alpha, the probability of type 1 error was set to 0.05 and the power was set to 0.8 which resulted in the probability of a type 2 error of 0.2, given that we limited to 20 participants per treatment, delta was estimated with this restriction.

ETHICS

Risk category: Risk greater than minimal.

Authorization will be requested from the Research Ethics Committee of the Hospital Central "[name] Prieto". The study will be performed according to the Mexican Official Standard for the conduct of clinical studies in humans NOM-012-SSA3-2012²¹, and international standards (Declaration of Helsinki²² and International Harmonized Guide (ICH) of Good Clinical Practices²³) The diagnostic maneuvers that will be used are considered of higher than minimal risk because it is an interventional study according to article 17 of the regulations of the General Law of Health²³ on Health Research.

In addition, it is a priority to safeguard the physical and mental integrity of the patient, and privacy is respected by maintaining the confidentiality of the data at all times during the research, as well as the data obtained at the end of it. The consent of the legal subjects will be obtained through a document specifying the objective of the study, the duration, as well as the methods and medications that they will receive randomly.

RESULTS

Eighty-seven patients were evaluated, of which only 33 patients were included in the study. In the Memantine group with 16 patients and 17 in the Sodium Valproate (VPA) group; only 27 patients concluded the study.

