Demographic data: In the Memantine group there were 13 women and three men, in the VPA group 13 women and four men. The average age of the patients in the Memantine group was 31.18 ± 10.94 years and those in the VPA group 31.58 ± 7.51 years ([Table 1](#)).

Migraine characteristics: In the Memantine group 62.5% (n=10) had a family history of migraine and in the VPA group 52% (n=9). The age of migraine onset in both groups was 18 years on average. Headache pain characteristics in the memantine group were pulsatile in 81.25% (n=13), hemicranial 87.5% (n=14), disabling activities of daily living 93.75% (n=15), with photophobia in 87.50% (n=14), sonophobia 100% (n=16), disabling activities of daily living 93.75% (n=15), nausea and vomiting in 87.5% (n=14) in the VPA group was pulsatile in 76.47% (n=13), hemicranial 76.47% (n=13), disabling activities of daily living in 94.12% (n=16) with photophobia in 94.12% (n=16), sonophobia 58.82% (n=10), nausea and vomiting in 100% (17). With respect to aura only present in three patients in the memantine group and in four in the VPA group. ([Table 1: Migraine characteristics](#).)

Primary objective: In the Memantine group with average migraine attacks before treatment of 5.31 (SD+1.54) per month in the three months before and after three months of treatment 0.93 (SD+1.49) per month, with a decrease of 4.21 (SD+1.76) migraine attacks $p <<0.001$ ([Figure 1](#)). ([Figure 1](#)). In the VPA group with pretreatment mean migraine attacks of 5.35 (SD+1.11) and after three months of treatment of 0.77 (SD+1.16) ([Figure 2](#)) with a decrease of 4.5 (SD+1.39) migraine attacks $p <<0.001$ ([Figure 3](#)).

[figure not shown]
[figure not shown]

[figure not shown]
Table 1 . Baseline characteristics of both groups.

Variable	Memantine	Sodium Valproate
Sex (%)		
Woman	13 (81.25%)	13 (76.47%)
Man	3 (18.75%)	4 (23.52%)
Average age	31.18 ± 10.94	31.58 ± 7.51
Family history of migraine (%)	10 (62.5%)	9 (52.94%)
Characteristics of migraine		
Type of pain (%)		
Pulsating	13 (81.25%)	13 (76.47%)
Oppressive	3 (18.75%)	4 (23.52%)
Pain location (%)		
Hemicranial	14 (87.5%)	13 (76.47%)
Holocranial	2 (12.5%)	4 (23.52%)
Photophobia No. (%)	14 (87.50%)	16 (94.12%)
Sonophobia No. (%)	16 (100%)	10 (58.82%)
Nausea and vomiting No. (%)	14 (87.5%)	17 (100%)
Incapacitates activities of daily living	15 (93.75%)	16 (94.12%)
Migraine without aura	13 (81.25%)	13 (76.47%)

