Migraine with aura	3 (18.75%)	4 (23.52%)

Secondary objectives. - Treatment response rate which is referred to as the decrease of equal or more than 50% of migraine days. In the Memantine group with pretreatment migraine days 4.3 (SD+ 1.93) and post treatment 0.23 (SD+ 0.44) with a mean decrease in migraine days of 3.9 (SD+ 1.89) $p <<0.001$. In the Sodium Valproate group with pretreatment migraine days 5.5 (SD+ 1.25) and post treatment 0.27 with mean decrease of migraine days 4.88 with (SD+ 1.29) $p <<0.001$ ([Figure](#))

4). In both groups the 27 patients presented a successful treatment response rate, in the Memantine group with a decrease in percentage of migraine days average 94% (SD+ 9.95) and in the Sodium Valproate group 93.18% (SD+ 14.50).

The intensity of migraine was evaluated with the Visual Analog Scale (VAS) pre and post treatment. In the Memantine group pre-treatment VAS 8.5 (SD+ 1.36) and post-treatment 4.28 (3.65) $p < 0.00014$. In the VPA group with pretreatment VAS 8.94(SD+ 0.87) and post treatment 2.5 (SD+ 0.87) $p < 0.0000012$.

Migraine disability assessed with MIDAS in the Memantine group with MIDAS mean pretreatment 60.87 (SD+ 25.22) and post-treatment 15.57 (SD+ 14.32) $p < 0.000004$. In the Sodium Valproate group with MIDAS pretreatment of 51.92 (SD+ 22.67) and post treatment 10.53 (SD+ 19.97) $p < 0.00002$ ([Figure 5](#)).

Figure 5. MIDAS pre- and post-treatment in both groups.

Side effects: The side effects presented by the patients were not severe in their totality, eight patients in the Memantine group presented non-severe side effects and seven patients in the sodium valproate group ([Table 2](#)), the most frequent in both groups being somnolence.

Table 2 . Side effects

	Memantine	Sodium Valproate
None		
Drowsiness		
Lack of concentration		0
Parasomnia	0	1
Dizziness		0
Total		

DISCUSSION

This is the first randomized double-blind pilot clinical trial comparing the efficacy and safety of memantine with a first-line treatment, sodium valproate.

With the objective of recruiting 40 patients as a pilot study, the Neurology outpatient clinic was suspended due to the COVID-19 pandemic, we finally managed to recruit 33 patients, 3 lost follow-up and 3 dropped out of the study due to COVID-19 and only 27 patients were included.

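### Reported migraine days conflict with reported attacks and with the 14 and 13 completers, so the statement that all 27 patients responded is not supported as printed.

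*Protocol*

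**What the plan says.** The Protocol defines response on days with migraine (List of definitions; Subjects and methods, Variables). The SAP lists response rate first among its secondary outcomes.

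The Summary states: "All 27 patients had a good response rate". Results, Secondary objectives, repeats it: "In both groups the 27 patients presented a successful treatment response rate". On the samples, the Summary says "27 of them concluded the study; 14 in the Memantine group and 13 in the Sodium Valproate group", and the opening of Results says "In the Memantine group with 16 patients and 17 in the Sodium Valproate (VPA) group; only 27 patients concluded the study". No denominator is attached to the day figures.

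The memantine day figures read: "In the Memantine group with pretreatment migraine days 4.3 (SD+ 1.93) and post treatment 0.23 (SD+ 0.44". For valproate the text gives 5.5 (SD 1.25) before and 0.27, without an SD, after.

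The memantine attack figures read: "In the Memantine group with average migraine attacks before treatment of 5.31 (SD+1.54) per month", and "after three months of treatment 0.93 (SD+1.49) per month, with a decrease of 4.21 (SD+1.76) migraine attacks". Valproate attacks are 5.35 (SD 1.11) before and 0.77 (SD 1.16) after.

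The Background describes migraine as "recurrent episodes of headache lasting from 4 to 72 hours". Entry requires at least 4 attacks a month in both documents.

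**The concern.** If each attack occupies part of at least one calendar day, and attacks seldom share a day, migraine days should be about as many as attacks or more. In three of the four comparisons they are clearly fewer. The post-treatment day means also do not look like averages over 14 and 13 people.

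A 100% response in both arms stands unqualified in the Summary and rests on this variable. If days were mislabelled, counted over another period or available for fewer patients, that claim has no visible basis. The attack data, which carry the primary outcome, do not supply one either.

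**Working it through.** **1. Attack figures against the stated samples.** Whole-number totals reproduce them:

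| Figure | Total / n |
|---|---|
| Memantine baseline 5.31 | 85/16 |
| Memantine after 0.93 | 13/14 |
| Memantine fall 4.21 | 59/14 |
| Valproate baseline 5.35 | 91/17 |
| Valproate after 0.77 | 10/13 |

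Baseline minus after in memantine is 4.38, not 4.21, but this only reflects 16 against 14 patients. The completers' baseline is (13 + 59)/14 = 5.14, and 5.14 − 0.93 = 4.21.

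**2. Day figures against the stated samples** (whole days, one month).
- Memantine after, 0.23 (SD 0.44): 3/13 = 0.231, and three ones with ten zeros give SD 0.4385. With n = 14 the nearest values are 3/14 = 0.214 (SD 0.426) and 4/14 = 0.286 (SD 0.469). Half days do not help: 3.5/14 = 0.25.
- Valproate after, 0.27: 3/11 = 0.273. With n = 13, 3/13 = 0.23 and 4/13 = 0.31; half days would allow 3.5/13 = 0.269. The mean percentage fall of 93.18% equals 1025/11.
- The valproate fall of 4.88 days fits 78/16 or 83/17, but no whole total over 11 or 13.

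**3. Memantine after treatment: attacks against days.** Three sets of 14 whole counts have total 13 and SD 1.49: (5,3,2,1,1,1), (5,2,2,2,2) and (4,4,2,2,1), the rest zero. Each has at least five patients with an attack. If one patient is missing from the day data, at least 8 attacks in at least four patients remain, against 3 days in three patients. At least one patient then has an attack and no migraine day.

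**4. Valproate after treatment.** Total 10 over 13 with SD 1.16 (1.1658, truncated) gives (4,2,1,1,1,1) or (3,3,2,1,1). Dropping the two highest leaves at least 4 attacks against 3 days. This conflict is mild.

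**5. Memantine baseline.** If every patient had at least 4 whole days, the SD is largest when all but one have exactly 4. With the total e above 4n, that SD is e/√n. For means rounding to 4.3 and n = 13 to 16, the maximum is n = 15, total 65: 5/√15 = 1.29. If the mean was truncated, n = 16, total 70 gives 6/√16 = 1.5. The stated SD is 1.93, so some patients had fewer than 4 days. Missing patients do not close the gap in means: if three absent patients each had 8 attacks, the other 13 average (85 − 24)/13 = 4.69 attacks, above 4.3 days.

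**6. Did every memantine completer halve their attacks?** Let b and p be a completer's attacks before and after. A sum of squares is (n − 1)SD² + total²/n:
- baseline, 16 patients: 15 × 1.54² + 85²/16 = 487.1, whole number 487;
- after, 14 patients: 13 × 1.49² + 13²/14 = 40.9, whole number 41;
- fall, 14 patients: 13 × 1.76² + 59²/14 = 288.9, whole number 289.

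The two non-completers had 85 − 72 = 13 attacks between them, so their squares sum to at least 6² + 7² = 85. The completers' Σb² is therefore at most 487 − 85 = 402. Since Σ(b − p)² = Σb² − 2Σbp + Σp², we get Σbp ≤ (402 + 41 − 289)/2 = 77. If all 14 had halved, b ≥ 2p would give Σbp ≥ 2 × 41 = 82. The two cannot both hold, so at least one completer did not halve. An exhaustive search with baseline at least 4 agrees, under the Protocol's 4–8 range and the SAP's 4–14: no solution has every completer halved, while solutions exist without that condition.

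**The case against.** Four counter-arguments carry weight.

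- **Counting rule.** The visible text does not say how the diary defined a migraine day. The diary form (Annex 3) is not in the text available, and the rule of counting every day of a long attack belongs to the MIDAS questionnaire. If days were accumulated duration, the ratios give about 19 and 6 hours per attack in memantine (4.3/5.31 × 24; 0.23/0.93 × 24) and 25 and 8 hours in valproate, all within 4 to 72 hours. A reader might infer that the variable cannot be days with migraine; the documents do not settle that. But accumulated duration is not the variable on which response is defined, so this reading does not rescue the claim.
- **Window and rounding.** Results mention three-month periods, and the documents sometimes truncate (4/17 is printed as 23.52%). A truncated three-month average, 10/42 = 0.238, would print as 0.23 with n = 14; values of 4/3, 1, 2/3 and 1/3 in four patients give SD 0.442. A firm ceiling of 26 responders is therefore not established. The same device does not yield 0.27 with n = 13.
- **Entry criterion.** The minimum of 4 concerns attacks, not days. Step 5 shows a conflict only if attacks rarely share a day.
- **Mixed samples.** Dividing 13 attacks by 3 days suggests about four attacks per day, but sets 14 patients against 13. With one patient missing, 8 attacks may remain (8/3 = 2.7). In valproate, two attacks on one day would reconcile 4 attacks with 3 days.

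It would also be wrong to say days are below attacks throughout: valproate baseline runs the other way. And response is a secondary outcome of a pilot.

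**Conclusion.** The point holds in limited form. The day figures disagree with the attack figures in memantine at both times and in valproate after treatment, most clearly in memantine after treatment: at least five patients with an attack, against three days in three patients. On whole-day monthly counts the post-treatment day means describe 13 and 11 patients, 24 in all, not 27. That count is conditional: half days would admit 13 valproate patients, and a truncated three-month average would admit 14 memantine patients.

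The printed figures do not identify the cause. Mislabelling, another window, missing patients and transcription error all remain possible, and under each the 27-of-27 statement lacks support as printed. The memantine attack data point the other way: at least one completer did not reach a 50% fall. That step assumes whole monthly counts, that 5.31 covers all 16 randomised, and that 0.93 and 4.21 cover the same 14 completers, as their arithmetic indicates. It concerns attacks, so it does not itself show a non-responder on days.

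**What to change.** State how a migraine day was counted, over what window and in how many patients per arm. Re-derive migraine days and 50% response patient by patient from the diaries already collected, checking each patient's days against attacks, and report responders with n for each arm. Report 50% response on attack counts alongside. Supply the missing SD for valproate days after treatment. Until this is done, do not state, in the Summary or in Results, that all 27 patients responded.

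The cost is re-tabulating data already held. The response rate may become less favourable.

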- 4. Adverse events to abortive treatment.
- 5. Infrequent migraine conditions: Ophthalmoplegic migraine, basilar migraine, hemiplegic, prolonged aura, migraine infarction.

The IHS defines response to treatment as a decrease equal to or greater than 50% in the frequency of migraine days compared to baseline.¹⁰

The American Academy of Neurology guideline for the prophylactic pharmacological treatment of episodic migraine classifies divalproate sodium, valproate sodium (VPA), topiramate, metoprolol and propranolol in level A (Drugs with established efficacy).¹¹

Valproic acid (2-propylpentanoic acid) was first synthesized in 1882 as an analog of valeric acid, which is naturally found in valerian. Valproic acid, sodium valproate or a mixture of the two (sodium divalproate), with mechanism of action characterized by increasing or enhancing γ -aminobutyric acid (GABA) neurotransmission, blockade of voltage-dependent sodium channels and T-type calcium channels.¹² In 2013 Cochrane conducted the review: Valproate for episodic migraine prophylaxis (Lindae et al)¹² where they evaluated 10 clinical trials. Two crossover clinical trials for sodium Valproate demonstrated a significant reduction in headache frequency compared to placebo (MD -4.31 95% CI -8.32 to -0.30) which shows us in clinical terms an approximate reduction of four headaches per 28 days. The Jensen 1994 study¹³ showed that sodium valproate is superior to placebo (OR 4.67; 95% CI 1.54 - 14.14), suggesting that patients are three times more likely to have a reduction equal to or greater than 50% in the frequency of headaches compared to placebo.¹³ The recommended dose for migraine is 500 to 1000 mg per day.¹¹ The most frequent adverse effects are: asthenia, fatigue, dizziness/vertigo, nausea, tremor and weight gain.¹²

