Recruitment was carried out from July 2019 to August 2020 in the outpatient service of Neurology, Referral and Emergency of the Central Hospital. Patients who met the inclusion criteria and signed the informed consent form participated in the study. At the time of recruitment, they will be randomized by computer by an external collaborator of wide experience, assigning them a number and an external collaborator will distribute them in one of the two groups. Double-blinding will be performed, both for the researcher and for the participant, the only one who knew which group they were assigned to was the one who performed the randomization.

A total of 4 visits were made, with a time interval of one month for each visit.

Visit 1 (Week 0): a clinical history was taken, a physical examination was performed, the informed consent form was signed (Annex 1), and the inclusion and exclusion criteria form (Annex 2) was filled out by the researcher. A "Migraine diary" (Annex 3) was provided to the patient where the migraine attacks were recorded to identify the baseline characteristics such as frequency, intensity, duration.

Visit 2 (Week 4): the patient was given the medication assigned by the corresponding randomization. Memantine or VPA was prescribed as an oral tablet at night for one week and then increased in the second week to one tablet in the morning and at night. The baseline MIDAS survey was performed to identify migraine disability. The baseline "Migraine Diary" was collected and a new "Migraine Diary" was provided.

Visit 3 (Week 8): Frequency of migraine attacks, adverse effects and tolerability of treatment were assessed by the investigator. The "Migraine Diary" was collected and a new "Migraine Diary" was provided. The corresponding medication was given for four weeks.

Visit 4 (Week 12): Visit 3 (Week 8): Migraine attack frequency, adverse effects and tolerability of treatment were assessed by the investigator. The "Migraine Diary" was collected and a new "Migraine Diary" was provided. The corresponding medication was given for four weeks.

Visit 5 (Week 16): Frequency of migraine attacks, adverse effects and tolerability of treatment were evaluated by the investigator. The "Migraine Diary" was collected. The MIDAS survey was performed again to assess post-treatment disability.

Financing

A donation of the pharmacological treatment Memantine and sodium Valproate was received from the Torrent Pharma Laboratory (Annex 5).

STATISTICAL ANALYSIS

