Being a carrier of systemic disease (infectious, immunological, or metabolic processes) or cardiovascular (myocardial, coronary, or valvular disease) prevents their participation in the study.

Primary outcomes

The primary outcome was the difference in change from baseline in the monthly attack frequency at week 12 between the two groups (using migraine diary).

Secondary outcomes

1. Evaluate the response rate to treatment.
2. Evaluate migraine disability using MIDAS (Migraine Disability Assessment) before and after treatment.
3. Identify adverse effects to sodium valproate and memantine.

Statistical analysis.

Statistical analysis

Descriptive statistical analysis of the variables of interest will be carried out.

For continuous variables, their research will be analyzed using the t-student test.

First, the number of participants (n) and the final analysis were calculated using R (56).

Alpha, the probability of a type 1 error was set to 0.05.

The power was set to 0.8, resulting in a type 2 error of 0.2.

Since we were limited to 20 participants per treatment, the delta was estimated with this restriction.

Since we were limited to 20 participants per treatment, the delta was estimated with this restriction.

Results

Table 1. Baseline Demographic and Clinical Characteristics

[figure not shown]
Characteristic	Memantine	Sodium Valproate	p
Female sex – no (%)	13(81.25%)	13 (76.47%)	
Male sex – no (%)	3 (18.75%)	4 (23.52%)	0.54*
Age	$31.18 \pm 10.94^{\$}$	$31.58 \pm 7.51^{\$}$	0.91*
A family history of migraine (%)	10 (62.5%)	9 (52.94%)	0.82*
Clinical characteristics			
Photophobia - no (%)	14 (87.50%)	16 (94.12%)	0.48*
Phonophobia - no (%)	16 (100%)	10 (58.82%)	0.60*
Nausea - no (%)	14 (87.5%)	17 (100%)	0.23*
Disability activities of daily living	15 (93.75%)	16 (94.12%)	0.74*
Migraine without aura	13 (81.25%)	13 (76.47%)	0.54*
Migraine with aura	3 (18.75%)	4 (23.52%)	

* Fisher's exact test

§ Plus-minus values are means \pm SD

PRIMARY OUTCOME

[figure not shown]
Monthly attack migraine frequency before and after treatment

Secondary outcome

Evaluate the response rate to the treatment

Figure 2. Days with migraine before and after treatment

Adverse Events

Table 2. Adverse Events According to Group

	Memantine (n=17)	Sodium Valproate (n=16)	Clinical severity CTCAE*
Any adverse event	8	7	
Somnolence	4	6	Grade 1-Mild
poor concentration	2	0	Grade 1-Mild
Parasomnia	0	1	Grade 1-Mild
Dizziness	2	0	Grade 1-Mild

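### Adverse effects may be undercounted: SAP Table 2 fits one effect per patient, and the available text describes no common symptom list and no weight measurement

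*Protocol*

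**What the plan says.** Identifying adverse effects of both drugs is a secondary objective in the Protocol and a secondary outcome in the SAP. The Protocol Summary makes the frequency and severity of adverse events the measure of safety.

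- **Counts.** Protocol Results, side effects: "eight patients in the Memantine group presented non-severe side effects and seven patients in the sodium valproate group". SAP Table 2 agrees (memantine, then valproate): "Any adverse event 8 7". Its effect rows include "Somnolence 4 6 Grade 1-Mild" and "poor concentration 2 0 Grade 1-Mild", then parasomnia 0 and 1, and dizziness 2 and 0. The Protocol Discussion restates the memantine rows (4, 2 and 2) as numbers of patients.
- **Expected valproate effects.** Protocol Background: "The most frequent adverse effects are: asthenia, fatigue, dizziness/vertigo, nausea, tremor and weight gain".
- **Collection.** Protocol Work Plan, Visit 3: "Frequency of migraine attacks, adverse effects and tolerability of treatment were assessed by the investigator". Visits 4 and 5 say much the same. The only examination described is at Visit 1: "a clinical history was taken, a physical examination was performed". Weight is not mentioned at any visit.
- **Conclusions.** The Protocol Summary calls adverse effects infrequent and of minimal severity. The SAP Conclusions call them frequent, though mild and transient.

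**The concern.** Two separate features raise doubt about the safety tables.

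First, when a patient can have more than one effect, the effect rows normally add up to more than the number of patients affected. Here they add up to exactly that number in both arms, over three monthly assessments. The Protocol's own Table 2 has None and Total rows, a layout that suits one category per patient. Second effects may therefore have been dropped.

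Second, the comparator's commonest effects, as the Protocol itself lists them, are absent from the comparator arm. One of them, weight gain, needs a measurement that the schedule does not describe.

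At stake is what the trial can say about tolerability, which the Justification names as a main cause of poor adherence to prophylaxis. The efficacy result is not affected.

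**Working it through.** **1. Row sums (SAP Table 2)**
- Memantine: 4 + 2 + 0 + 2 = 8; printed total 8.
- Valproate: 6 + 0 + 1 + 0 = 7; printed total 7.

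Both match exactly. The Protocol calls these totals patients, so no patient is shown with two effects.

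**2. How surprising is no overlap?** Assume that effects fall independently among patients, with the printed row counts and the Protocol's arm sizes (16 and 17).
- Memantine: C(12,2)/C(16,2) × C(10,2)/C(16,2) = 66/120 × 45/120 = 0.206.
- Valproate: 11/17 = 0.647.
- Both: 0.206 × 0.647 = 0.13. With the SAP Table 2 arm sizes (17 and 16) it is 0.232 × 0.625 = 0.14.

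**3. The six effects named in the Background, valproate arm**
- Asthenia, fatigue, nausea, tremor and weight gain have no row in SAP Table 2.
- Dizziness is 0 on valproate and 2 on memantine.
- For any one effect, 0 of 17 has an exact two-sided 95% upper limit of 1 − 0.025^(1/17) = 19.5%.
- The documents give no incidence figures, so a range is assumed. If all six effects were independent with the same true rate p, the chance of seeing none of them in n patients is (1 − p)^(6n):

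| p | n = 17 (randomised) | n = 13 (completers) |
|---|---|---|
| 2% | 13% | 21% |
| 3% | 4.5% | 9% |
| 5% | 0.5% | 1.8% |
| 10% | 0.002% | 0.03% |

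**4. Are steps 1 and 3 linked?** Under the Protocol's arm size, 17 − 7 = 10 valproate patients have no recorded effect. Keeping one effect per patient would not have hidden nausea or tremor in any of those ten. The two observations stand apart.

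**5. Arm sizes.** SAP Table 2 heads the arms 17 (memantine) and 16 (valproate). The Protocol Results give 16 and 17, and the Table 1 percentages in both documents agree with the Protocol: 13/16 = 81.25% and 13/17 = 76.47%. Any adverse event is 8/16 = 50% against 7/17 = 41% (Fisher p = 0.73), or 8/17 = 47% against 7/16 = 44% (p = 1.00) with the SAP headings.

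**The case against.** The strongest reply is that nothing here demonstrates undercounting. No overlap is unremarkable in the valproate arm (0.65) and has a joint chance of 0.13. A true rate of up to about 19% for any one effect is compatible with none in 17. The six-effect calculation rests on assumed rates and on independence, which is doubtful for effects as close as asthenia and fatigue. The investigator assessed adverse effects at three visits, the Protocol defines them and their severity, and the SAP grades each by CTCAE v5.0. Most cells of Protocol Table 2 are unreadable, so its layout is weak evidence. Annexes 1 to 3 (consent form, criteria form, migraine diary) were not in the available text, and a symptom list or a weight field there cannot be excluded.

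All of this stands, and it rules out several stronger readings that a reader might infer:
- That the tables do undercount. This is possible but not shown.
- That one-per-patient counting explains the missing valproate effects. Ten patients had no recorded effect, so it cannot.
- That the six effects occurred in nobody. Dizziness is recorded in two memantine patients.
- That effects were only volunteered, or that weight was taken at Visit 1 and then dropped. The text says neither.
- That one drug was favoured. No direction is shown.

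The objection does not answer the gap in the schedule. As described, it gives no means of reliably detecting weight gain, and the table does not say whether a patient could appear in more than one row.

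**Conclusion.** The point holds as a modest, inexpensive improvement. The row totals equal the numbers of patients with any event (8 and 7), which suggests one effect per patient without proving it (chance of no overlap about 0.13, assuming independence). None of the six effects that the Background names is recorded in the valproate arm. That becomes unlikely only if each has a true rate of roughly 3 to 5% or more, an assumed figure that the documents do not supply. No common symptom list and no weight measurement are described in the available text, so weight gain could not be reliably detected and adverse effects may be undercounted. No corrected count can be derived, and neither the size nor the direction of any difference between arms is established.

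Two contradictions in the documents bear directly on the safety statement: the reversed arm sizes in SAP Table 2, and the opposite descriptions of frequency in the Protocol Summary and the SAP Conclusions.

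**What to change.** 1. **Schedule.** Record weight at Visits 2 and 5 and report the change by arm. At Visits 3, 4 and 5 ask every patient, blinded and in the same way, about the six effects listed in the Background. The cost is a scale reading and a short list at visits that already exist; the downside is somewhat higher recorded rates in both arms. The study has already been run, so unless these data were collected, this applies to the larger trials that the Limitations section calls for.
2. **Table 2, now.** First reconcile the arm sizes (17 and 16, or 16 and 17). Then check the Visit 3 to 5 records for second effects. Report separately the patients with each effect (a patient may appear in several rows), the patients with at least one effect, and the number of events. If there were no second effects, one sentence saying so settles the matter. The cost is re-tabulating existing records.
3. **Conclusion, now.** Where weight and a common list were not collected, limit the safety conclusion to effects as reported to the investigator. Reconcile the description as infrequent with the description as frequent but mild, and both with the counts, 8/16 and 7/17 on the Protocol's arm sizes. The cost is a change of wording.
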